### 7.6.3 Blood Donation

Patients should not donate blood while participating in this study, or for at least 90 days following the last infusion of durvalumab.

**Table 7: Highly Effective Methods of Contraception (<1% Failure Rate)**

• Barrier/Intrauterine methods	• Hormonal Methods
• Copper T intrauterine device	• Implants: Etonogestrel-releasing implants: e.g. Implanon® or Norplant®
• Levonorgestrel-releasing intrauterine system (e.g., Mirena®) a	• Intravaginal: Ethinylestradiol/etonogestrel-releasing intravaginal devices: e.g. NuvaRing®
	• Injection: Medroxyprogesterone injection: e.g. Depo-Provera®
	• Combined Pill: Normal and low dose combined oral contraceptive pill
	• Patch: Norelgestromin/ethinylestradiol-releasing transdermal system: e.g. Ortho Evra®
	• Minipill: Progesterone based oral contraceptive pill using desogestrel: Cerazette® is currently the only highly effective progesterone-based

a This is also considered a hormonal method

## 7.7 Duration of Therapy and Criteria for Removal from Study

In the absence of treatment delays, chemotherapy plus Durvalumab will continue for 4 cycles with subsequent single-agent Durvalumab continuing indefinitely, or until one of the following criteria applies:

- Disease progression
- Intercurrent illness that prevents further administration of treatment,
- Unacceptable adverse event(s),
- Subject decides to withdraw from the study, or
- General or specific changes in the subject's condition render the subject unacceptable for further treatment in the judgment of the investigator.

Subjects may continue on single-agent Durvalumab after disease progression by RECIST criteria if this is felt to be beneficial by the treating medical oncologist. RECIST progression should be confirmed on 2 imaging scans at least 4 weeks apart, though this is not required.

### **7.8 Duration of Follow Up**

Subjects will be followed for 2 years after removal from study or until death, whichever occurs first. Subjects removed from study for unacceptable adverse events will be followed until resolution or stabilization of the adverse event.

### **7.9 Study Intervention/Follow-up Compliance**

The study will be conducted as described in the final IRB-approved protocol. Adherence to the protocol will be assessed and verified by the research study team, the DSMB, and, if needed, by the medical monitor. Repeated attempts will be made to get subjects to return for study follow-up appointments; however, after 3 months subjects will be considered “lost to follow-up” and no longer participating in the study.

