#### **6.1.3 Follow-up Phase: From Time of Progression to Withdrawal from Study or Death**

- Interval Medical History
  - Every 28 days ( $\pm$  7 days) for the first 84 days; then every 84 days ( $\pm$  7 days)
- Concurrent Medications
  - Every 28 days ( $\pm$  7 days) for the first 84 days; then every 84 days ( $\pm$  7 days)
- Vital signs including Height and Weight
  - Every 28 days ( $\pm$  7 days) for 84 days
- Physical Exam
  - Every 28 days ( $\pm$  7 days) for 84 days
- Labwork: CBC with differential; Serum Chemistry with Liver Function Tests; Thyroid Function Panel
  - Every 28 days ( $\pm$  7 days) for 84 days
- Adverse Event Evaluation
  - Every 28 days ( $\pm$  7 days) for the first 84 days; then every 84 days ( $\pm$  7 days)

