## **8. Study Intervention Discontinuation and Participant Discontinuation/Withdrawal**

### **8.1 Discontinuation of Study Intervention**

An individual subject who is discontinued from the study will not receive any further investigational product. An investigator may discontinue a participant from the study for the following reasons:

1. If any clinical adverse event (AE), laboratory abnormality, or other medical condition or situation occurs such that continued participation in the study would not be in the best interest of the participant
2. Disease progression which requires discontinuation of the study intervention
3. If the participant meets an exclusion criterion (either newly developed or not previously recognized) that precludes further study participation because continuing investigational therapy might constitute a safety risk
4. Participant unable to receive radiation, chemotherapy, or ICB therapy for 12 weeks.
5. Withdrawal of consent or *participant lost to follow-up after several attempts to contact subject to schedule study visit.*
6. Adverse event related to radiation or chemotherapy that, in the opinion of the investigator or the sponsor, contraindicates further treatment with these modalities
7. Pregnancy or intent to become pregnant

8. Adverse event related to durvalumab that is Grade  $\geq 3$ , with the exception of toxicities that do not meet criteria for discontinuation as per guidelines in Appendix B or per NCCN Clinical Practice Guidelines in Oncology Management of Immunotherapy-Related Toxicities.
9. Grade  $\geq 3$  infusion reaction
10. Subject noncompliance that, in the opinion of the investigator or sponsor, warrants discontinuation, such as refusal to adhere to scheduled visits or initiation of alternative anticancer therapy including another investigational agent

Discontinuation from study intervention does not mean discontinuation from the study, and remaining study procedures should be completed as indicated by the study protocol. If a clinically significant finding is identified (including, but not limited to, changes from baseline) after enrollment, the investigator or qualified designee will determine if any change in participant management is needed. Any new clinically relevant finding will be reported as an adverse event (AE).

The data to be collected at the time of study intervention discontinuation will include the following:

- Interval Medical History
- Concurrent Medications

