## **8.3 Lost to Follow Up**

A participant will be considered lost to follow-up if he or she fails to return for scheduled visits for 3 months and is unable to be contacted by the study site staff.

The following actions must be taken if a participant fails to return to the clinic for a required study visit:

- The site will attempt to contact the participant and reschedule the missed visit within 14 days and counsel the participant on the importance of maintaining the assigned visit schedule and ascertain if the participant wishes to and/or should continue in the study.
- Before a participant is deemed lost to follow-up, the investigator or designee will make every effort to regain contact with the participant (where possible, 3 telephone calls and, if necessary, a certified letter to the participant's last known mailing address or local equivalent methods). These contact attempts should be documented in the participant's medical record or study file.
- Should the participant continue to be unreachable, he or she will be considered to have withdrawn from the study with a primary reason of lost to follow-up.

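### Section 7.9 ends participation for subjects who stop returning but can still be reached, against sections 8.3 and 7.8; if it is applied, vital status for OS may go uncollected, with no rule for the gap

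*Combined protocol and SAP*

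**What the plan says.** Four places in the combined protocol and SAP bear on when a subject who stops attending leaves the study.

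- Section 7.9 (follow-up compliance) promises repeated attempts to get subjects back to appointments, then says that "after 3 months subjects will be considered “lost to follow-up” and no longer participating in the study". Being out of contact is not part of the condition.
- Section 8.3 (the dedicated section) applies the label to a subject who "fails to return for scheduled visits for 3 months and is unable to be contacted by the study site staff". It adds that "Before a participant is deemed lost to follow-up, the investigator or designee will make every effort to regain contact with the participant", by calls and if necessary a certified letter. Only then: "Should the participant continue to be unreachable, he or she will be considered to have withdrawn from the study".
- Section 7.8: "Subjects will be followed for 2 years after removal from study or until death, whichever occurs first".
- Section 6.1.3 is titled "Follow-up Phase: From Time of Progression to Withdrawal from Study or Death", so its visits stop at withdrawal.

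Section 8.1 item 5 also lists, among the reasons for discontinuing a subject, "participant lost to follow-up after several attempts to contact subject to schedule study visit", without a time limit.

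Section 10.2 defines 12-month OS as the proportion alive at 12 months and estimates median OS by Kaplan-Meier. Section 12.4.2 analyses the 12-month rate as a binomial proportion. Neither section says how unknown vital status is handled or when OS is censored.

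**The concern.** Take a subject who has progressed, no longer comes to clinic, and answers the telephone. Under 7.9 that subject is out of the study after 3 months. Under 8.3 the subject is not lost, and 7.8 points to continued follow-up until death or 2 years. A site following either text is complying with the protocol.

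OS depends on follow-up after progression. The historical 12-month PFS in section 2.1 is 18%, so most subjects would have had a PFS event before the 12-month OS time point. Subjects who have progressed have a higher hazard of death than those who have not. Censoring them early can push a Kaplan-Meier curve upward, and the binomial 12-month proportion depends on a convention that the plan does not state. OS is also read against the historical trial named in section 3.2. Vital status that was not collected at the time may not be fully recoverable later.

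**Working it through.** **1. The texts side by side, for a subject not returning for 3 months**

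| Situation | 7.9 | 8.3 | 7.8 |
|---|---|---|---|
| Cannot be contacted | lost, participation ends | lost, treated as withdrawn | follow-up for 2 years or until death |
| Can be contacted | lost, participation ends | not lost | follow-up for 2 years or until death |

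The conflict between 7.9 and 8.3 lies in the second row.

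**2. The plan's own sample size, to see whether it is touched**

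Section 12.1: 18% against 38% 12-month PFS, two-sided 0.05, 80% power.

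n = [(1.960·√(0.18·0.82) + 0.842·√(0.38·0.62)) / 0.20]² = 33.7, rounded up to 34; power at 34 is 80.3%. The planned 34 reproduces. It has no OS or loss-to-follow-up input, so this point does not change it.

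**3. Illustration for OS if 7.9 is applied**

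Inputs:
- PFS exponential with 18% at 12 months (section 2.1): λ = −ln(0.18)/12 = 0.1429 per month.
- Survival after progression exponential with median 6 months, the top of the 3–6 months in section 2.4: μ = ln 2/6 = 0.1155 per month. This choice gives a simulated median OS of 13.1 months, close to the 13.0 in section 2.1.
- Assumption, not in the documents: a share f of subjects stops attending at progression but stays reachable; f = 20%, range 10–30%. Those alive 3 months after progression are dropped at that point.

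True 12-month OS:
S = (λe^(−12μ) − μe^(−12λ))/(λ − μ) = (0.1429·0.25 − 0.1155·0.18)/0.0274 = 54.5%.

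Probability that a non-attender is dropped before month 12:
U = (1 − e^(−9λ))·e^(−3μ) = 0.724·0.707 = 0.512.

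Probability that a non-attender is dropped before month 12 and is in fact alive then:
A = λe^(−12μ)(1 − e^(−9(λ−μ)))/(λ − μ) = 0.285.

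So 0.285/0.512 = 56% of the unknowns are truly alive, close to the overall 54.5%.

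Unknown share = fU. Unknowns counted as alive: S + f(U − A). Unknowns excluded: (S − fA)/(1 − fU). Kaplan-Meier values come from simulating 1,000,000 subjects.

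| f | Unknown at month 12 | Counted as alive | Excluded | Kaplan-Meier at 12 months | Median OS (months) |
|---|---|---|---|---|---|
| 0 | 0% | 54.5% | 54.5% | 54.5% | 13.1 |
| 10% | 5.1% | 56.8% | 54.5% | 55.3% | 13.3 |
| 20% | 10.2% | 59.1% | 54.4% | 56.2% | 13.6 |
| 30% | 15.4% | 61.3% | 54.3% | 57.2% | 13.9 |

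Standard error of the 12-month proportion at N = 34: √(0.545·0.455/34) = 8.5 points.

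**4. Bounds without a survival model**

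Suppose 42 are treated and 22 are alive at 12 months (52.4%), and k reachable subjects are dropped from the proportion. If all k were alive the estimate is (22 − k)/(42 − k); if all k were dead it is 22/(42 − k).

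- k = 2: 50.0% to 55.0%
- k = 4: 47.4% to 57.9%
- k = 8: 41.2% to 64.7%

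The error can go either way. If vital status is ascertained, the estimate stays at 52.4%. The values of k are assumptions.

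**The case against.** The strongest reply is that 8.3 is the dedicated section, 7.8 stands directly above 7.9, and 8.1 says that stopping study intervention is not leaving the study. On that reading 7.9 is a loose summary and nothing is lost. It is a reasonable reading, and it is why the OS loss has to be stated conditionally. It does not remove the conflict: no precedence is given, and 7.9 plainly ends participation.

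Three stronger readings are tempting and are not supported.

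- A reader might count three definitions of loss to follow-up. Section 8.1 item 5 is a reason for discontinuation, not a definition. There are two conflicting definitions.
- A reader might infer that the 3-month clock clashes with the visit schedule. After progression, history and adverse events are collected every 28 days "for the first 84 days; then every 84 days", each ±7 days, so two compliant visits could be 84 + 7 + 7 = 98 days apart, and a 14-day rescheduling window after a visit missed at day 91 would close at day 105. This assumes that the clock starts at the last attended visit. Section 7.9 speaks of repeated attempts to bring the subject back, and 8.3 of failing to return for scheduled visits. Both presuppose a missed visit, so a compliant subject is not caught, and 14 days fits within 3 months of a missed visit.
- A reader might infer that the 12-month OS rate will be inflated. That needs unknowns to be counted as alive, which no section says. Excluding them leaves the proportion almost unchanged in the model.

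Two further objections stand. Beyond the first 84 days after progression, section 6.1.3 lists only history, medications and adverse events, none of which inherently requires attendance. The model also treats every PFS event as a progression followed by further survival, although section 10.1 counts deaths too, so it overstates the pool at risk.

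**Conclusion.** The point holds as a conflict of wording with a conditional effect on a secondary endpoint. Section 7.9 contradicts 8.3 on whether a reachable subject who does not attend is lost, and it sits against the continued follow-up in 7.8. If 7.9 is applied, OS loses obtainable data and the plan does not say how to treat the gap.

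With 10–30% reachable non-attenders, Kaplan-Meier 12-month OS rises by about 1–3 points and the median by about 0.2–0.8 months. The 12-month proportion moves by 0.2 points or less if unknowns are excluded and by about 2–7 points if they count as alive. These figures rest on exponential times, a 6-month median survival after progression and an assumed non-attendance rate. They are modest against a standard error of 8.5 points. OS is estimated with confidence intervals and not tested, and the sample size of 34 evaluable (42 enrolled) for PFS is not affected. The correction is still worth making because it costs little.

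**What to change.** - In 7.9, replace the 3-month sentence with a reference to 8.3: a subject is lost only after 3 months of missed scheduled visits and when not contactable after the contact steps in 8.3.
- In 8.1 item 5, refer to 8.3 for the meaning of lost to follow-up.
- State that subjects who do not attend but can be reached by telephone, through the treating physician or by chart review stay in survival follow-up under 7.8.
- In 10.2 or 12.4.2, add a line on OS censoring and on how subjects of unknown status enter the 12-month proportion.

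The cost is a few sentences of protocol text and a telephone or chart check of vital status at time points already scheduled. Treatment, visits and sample size do not change.

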## **8. Study Intervention Discontinuation and Participant Discontinuation/Withdrawal**

### **8.1 Discontinuation of Study Intervention**

An individual subject who is discontinued from the study will not receive any further investigational product. An investigator may discontinue a participant from the study for the following reasons:

1. If any clinical adverse event (AE), laboratory abnormality, or other medical condition or situation occurs such that continued participation in the study would not be in the best interest of the participant
2. Disease progression which requires discontinuation of the study intervention
3. If the participant meets an exclusion criterion (either newly developed or not previously recognized) that precludes further study participation because continuing investigational therapy might constitute a safety risk
4. Participant unable to receive radiation, chemotherapy, or ICB therapy for 12 weeks.
5. Withdrawal of consent or *participant lost to follow-up after several attempts to contact subject to schedule study visit.*
6. Adverse event related to radiation or chemotherapy that, in the opinion of the investigator or the sponsor, contraindicates further treatment with these modalities
7. Pregnancy or intent to become pregnant

8. Adverse event related to durvalumab that is Grade  $\geq 3$ , with the exception of toxicities that do not meet criteria for discontinuation as per guidelines in Appendix B or per NCCN Clinical Practice Guidelines in Oncology Management of Immunotherapy-Related Toxicities.
9. Grade  $\geq 3$  infusion reaction
10. Subject noncompliance that, in the opinion of the investigator or sponsor, warrants discontinuation, such as refusal to adhere to scheduled visits or initiation of alternative anticancer therapy including another investigational agent

Discontinuation from study intervention does not mean discontinuation from the study, and remaining study procedures should be completed as indicated by the study protocol. If a clinically significant finding is identified (including, but not limited to, changes from baseline) after enrollment, the investigator or qualified designee will determine if any change in participant management is needed. Any new clinically relevant finding will be reported as an adverse event (AE).

The data to be collected at the time of study intervention discontinuation will include the following:

- Interval Medical History
- Concurrent Medications
- Vital signs including Height and Weight
- Physical Exam
- Labwork: CBC with differential; Serum Chemistry with Liver Function Tests; Thyroid Function Panel
- Adverse Event Evaluation

## **8.2 Participant Discontinuation/Withdrawal from the Study**

Participants are free to withdraw from participation in the study at any time upon request.

The reason for participant discontinuation or withdrawal from the study will be recorded on the Case Report Form (CRF). Subjects who sign the informed consent form but do not receive the study intervention may be replaced. Subjects who sign the informed consent form and receive the study intervention, and subsequently withdraw, or are withdrawn or discontinued from the study, will not be replaced.

## **8.3 Lost to Follow Up**

A participant will be considered lost to follow-up if he or she fails to return for scheduled visits for 3 months and is unable to be contacted by the study site staff.

The following actions must be taken if a participant fails to return to the clinic for a required study visit:

- The site will attempt to contact the participant and reschedule the missed visit within 14 days and counsel the participant on the importance of maintaining the assigned visit schedule and ascertain if the participant wishes to and/or should continue in the study.
- Before a participant is deemed lost to follow-up, the investigator or designee will make every effort to regain contact with the participant (where possible, 3 telephone calls and, if necessary, a certified letter to the participant's last known mailing address or local equivalent methods). These contact attempts should be documented in the participant's medical record or study file.
- Should the participant continue to be unreachable, he or she will be considered to have withdrawn from the study with a primary reason of lost to follow-up.

## 9. Correlative/Special Studies

### 9.1 Tumor-immune microenvironment and the T-cell response

These studies will be done in the laboratory of [name], MD at WCM.

A comprehensive approach is proposed to analyze immunological changes that reflect both local and systemic responses, and general immune activation as well as tumor antigen-specific T cell responses. To this end, serial blood samples (50-ml) will be collected for serum and peripheral blood mononuclear cells (PBMC): at baseline, day 43, day 85 (at response evaluation) and thereafter every 8 weeks and at progression. Small aliquots of PBMC will be used ex vivo for preparation of DNA and RNA, and the remainder preserved frozen until evaluation by flow cytometry and/or by functional assays. Tumor tissue will be obtained at baseline, at day 85 and at progression from patients who consent to optional biopsies. Three 18G cores will be allocated for the following: DNA and RNA isolation (snap frozen), histology and multiplex imaging (fixed in formalin), and for generation of organoids by the EIPM Ex-vivo Lab (see section 9.2.1).

Flow cytometry analysis of circulating PBMC: Cryo-preserved PBMC isolated from serially collected blood following standardized SOPs, will be analyzed by multi-parameter flow cytometry. Specifically, levels of regulatory T cells (Tregs), will be monitored, and T cells (CD3+CD4+ and CD3+CD8+) analyzed for markers of naïve, effector and central memory phenotype (CD45RA/CCR7), proliferation (Ki67), and activation/exhaustion (CD25, CD137, PD-1, Tim-3, CTLA-4, and LAG3). Myeloid cells will be investigated for the expression of granulocytic and monocytic MDSC markers, and for the expression levels of MHC-I and MHC-II molecules, costimulatory and co-inhibitory molecules, including PD-L1. We will measure Ki67+PD-1+ CD8 T cells with an effector-like phenotype (HLA-DR+CD38+Bcl-1low) since they have been shown to be predictive of response in lung cancer patients treated with anti-PD-1 when increased within 4 weeks of treatment start from baseline by two to seven-fold .

Soluble markers: Serum/plasma levels of multiple chemokines and cytokines reflecting inflammatory and immune responses (IL-6, IL-10, IL-2, IFN- $\gamma$ , CXCL10/11, TNF $\alpha$ , CCL2, CCL5, etc.) will be measured using the human cytokine array (R&D Systems). We will also use a sensitive ELISA assay (Cat 41415-1, PBL assay Science) to measure the levels of serum IFNb since this cytokine is mechanistically relevant to the immunogenicity of SBRT . In addition, other cytokines and soluble factors that can be increased by RT may be associated with immune suppression (e.g., soluble MICA/B, soluble CD73) .

Whole Exome Sequencing (WES) and Neoantigen prediction will be performed as we have previously described . Briefly, DNA isolated from tumor and from PBMC (normal tissue control) will

be used for WES performed by the genomics core at WCM. Baseline tumor and PBMC WES data will be used in VarScan2 to detect somatic variants. Variants with somatic p-value (SPV) < 0.05 are considered statistically significant. Optitype algorithm will be used for HLA genotyping . The VCF files containing somatic mutations will be subjected to standard VEP, Downstream, and Wildtype annotations, and filtered for frameshift and missense mutations . Additionally, variant allele frequency (VAF) data will be generated using bamreadcount. The NetMHC and NetMHCpan algorithms will be used to predict patient-specific MHC-I binding for all possible 8-11 amino-acid long variant and corresponding wildtype peptide chains spanning the mutation using the pVAC-seq pipeline . Candidate neoepitopes will be synthesized and tested in vitro for recognition by the patients' T cells isolated from blood in ELISPOT assays.

TCRB CDR3 sequencing and repertoire analysis. Amplification and sequencing of TCRB CDR3 regions will be performed using the Adaptive Biotechnologies ImmunoSEQ platform . We have experience using this platform to analyze the expansion of TCR repertoire induced by treatment with RT and anti-CTLA-4 in mice  and in patients .

Multiplex imaging by mass cytometry using the Hyperion Imaging System: The Hyperion™ Imaging System brings together imaging capability with proven CyTOF® technology to facilitate Imaging Mass Cytometry™ applications. This allows highly multiplexed IHC enabling the simultaneous analysis of up to 37 protein markers . Over 60 metal-labeled antibodies are currently commercially available (Fluidigm) and have been optimized to detect markers in immuno-oncology pathways and cancer. Fluidigm also provides metal-labeling kits to prepare additional custom antibodies. We will use the Maxpar® Complete Human T Cell Immuno-oncology Panel Set to characterize infiltrating T cells. This panel has been validated and provides information about naïve, central memory, effector memory and effector CD4 and CD8 T cells, naïve and memory Tregs, Th1 and Th2 T cells, activation and homing status, and checkpoint expression. Additional panels will be used to characterize myeloid populations , and B cells, depending on the initial findings. Data deconvolution will be performed by [name], a co-investigator in this protocol.

